#### the patient's last follow-up

**Death:** the frequency distribution of deaths will be presented according to the reason:

- Adverse event
- Progression
- Other cause

#### 9 LIST OF TABLES AND TABLE OF CONTENTS

Table/Graph number			Table/Graph title					
1.			Included and evaluable population					
2.			Descriptive analysis					
	.1		Demographic and disease information					
		.1	Age					
		.2	Time from diagnosis and from the advanced diagnosis of the disease					
		.3	Gender					
		.4	ECOG at time of diagnosis, Heng prognostic criteria and site of metastasis					
		.5	Histological type					
		.6	Smoking					
	.2		Dosage and treatment regimen of tyrosine kinase with which the patient begins treatment					
3.			Analysis of evolution					
	.1		Presence of palmar-plantar erythrodysesthesia of any grade (month 3, month 6, month 9)					
		.1	Association between medication intake habits and evolution of hand- foot syndrome (every three months)					
		.2	Association between dose changes and evolution of hand-foot syndrome (every three months)					
		.3	Association between dose, treatment regimen received and the evolution of hand-foot syndrome (every three months)					
		.4	Association between temporary treatment interruptions and evolution of hand-foot syndrome (every three months)					
	.2		Presence of fatigue of any grade (baseline, month 3, month 6, month 9)					
		.1	Association between daytime rest habit and fatigue evolution (every three months)					
		.2	Association between daytime physical exercise and fatigue evolution (every three months)					
		.3	Association between daytime medication-taking habits and fatigue evolution (every three months)					
		.4	Association between daytime dose changes and fatigue evolution (every three months)					
		.5	Association between doses, daytime treatment regimen and fatigue evolution (every three months)					

CT24-GSOP-SD-GL04 NI Study SAP Template; Template Version 1.0, Effective 31-Dec-2013 Page 23 of 29

PFIZER CONFIDENTIAL

	.6	Association between temporary daytime interruptions and fatigue evolution (every three months)
	3	Data from the patient diary
	.1	Daytime rest (weekly)
	.2	Physical exercise (weekly)
	.3	Has taken the medication (weekly)
•-	4	Quality of life (FACIT_Fatigue) (every six weeks)
	.1	Association between daytime habit and evolution on the Facit_Fatigue (every six weeks)
	.2	Association between daytime physical exercise and evolution on the Facit_Fatigue (every six weeks)
	.3	Association between daytime medication-taking habits and evolution on the Facit_Fatigue (every six weeks)
	.4	Association between daytime dose changes and evolution on the Facit_Fatigue (every six weeks)
	.5	Association between doses, daytime treatment regimen and evolution on the Facit_Fatigue (every six weeks)
	.6	Association between temporary daytime interruptions and evolution on the Facit_Fatigue (every six weeks)
.4	5	Treatment, dose changes and temporary interruptions
· ·	7	Efficacy analysis
	.1	Number of treatment cycles received
	.2	Best response rate achieved with first-line treatment
	.3	ORR, DOR
	.4	Time on treatment and time to best response
	.5	Time to Treatment Failure (TTF)
	.6	Progression-free survival (PFS)
	.7	Reason for termination of treatment and reason for death

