In the pivotal phase III clinical trial involving sunitinib, 19% of patients discontinued treatment due to side effects and 38% of patients had to temporarily interrupt treatment, while 50% of patients had to reduce the standard dose in order to control adverse events. In fact, temporary dose interruptions are a strategy that is provided for in the summary of product characteristics for this purpose.

The most common grade 3-4 toxicity was hypertension (12%), followed by fatigue (11%), diarrhoea (9%) and HFS  $(9\%)^{4,7}$ .

In the sunitinib expanded access programme, 8% of patients discontinued treatment due to serious adverse events while 30% required dose reductions due to toxicity.

Pazopanib: 19% of cytokine-pretreated patients discontinued treatment versus 12% of treatment-naive patients.

10% of patients being treated with sorafenib stopped treatment due to side effects in the pivotal trial.

Although the therapeutic goal in the treatment of metastatic renal cell carcinoma is to prolong the survival of patients, it is equally important to keep treatment-related toxicities as low as possible in order to achieve patient adherence to treatment, thereby maximising dose intensity, which is the determining factor for obtaining better results in the long term. The high incidence of dose reduction and treatment interruptions due to adverse events could lead to decreased plasma drug exposure and reduced clinical benefit. The drug's tolerability may be a barrier when it comes to maximising the potential efficacy of therapy.

Therefore, maintaining the dose is a challenge, with side effects such as fatigue, diarrhoea, hand-foot syndrome (HFS) or hypertension. In fact, fatigue and diarrhoea are the most worrying symptoms when questioning patients, to such an extent that 50-75% of patients receiving treatment complain about some degree of asthenia, although only 7-11% of cases interfere with the activities of daily living.

In studies, TKI-related fatigue is highly variable in both degree and duration, although it is generally mild to moderate. In the case of sunitinib, this is especially significant since

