## 4 HYPOTHESIS TESTING

The statistical significance value is set to p<0.05 The SPSS statistical package, V19.0 or later will be used.

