#### 5 ANALYSIS POPULATION

#### 5.1 FULL ANALYSIS SET

Plans are to include 100 patients in the study to receive first-line treatment over the course of 18 months at 35 sites.

This is a descriptive study; therefore, a specific number of patients is not required to calculate the sample size.

In order to study the fatigue-related quality of life of patients who are taking a tyrosine kinase inhibitor, evaluated using the validated 13-item FACIT-Fatigue scale for patients with metastatic renal cancer on Spanish, the inclusion of 100 patients with metastatic renal carcinoma who are about to receive first-line treatment with a tyrosine kinase inhibitor and who meet the screening criteria of the study is proposed.

This sample size will allow us to estimate percentages of patients with fatigue (severe/non-severe) during follow-up, with a 95% level of significance and an estimated proportion of 10%, assuming a discontinuation rate of 5%.

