## • Has taken the medication:

- In the morning (between 7 am and 12 noon)
- In the afternoon (between 1 pm and 7 pm)
- At night (between 8 pm and 6 am)
- I have not taken any medication this week

For each one of the weekly habits described above, a summary calculation will be made (after three months) of each patient's habits in terms of daytime rest, physical exercise and taking their medication, taking the options marked with greater frequency in the last 12 weeks into account.

FACIT\_Fatigue: The main measures of centrality and dispersion measures will be calculated (mean, standard deviation, median, minimum, maximum, IR and 95%CI ) from the score obtained in the FACIT\_Fatigue quality of life scale, calculated as described in ANNEX 1. The absolute and relative frequency of patients with severe fatigue, being those with a score of less than 30 points on the FACIT\_Fatigue scale, will also be presented.

For each one of the evolution visits (week 6, week 12, week 18, week 24, week 30 and week 36), a study will be performed to ascertain whether significant changes have occurred in fatigue-related quality of life versus the previous evaluation, and defined as:

- **Improvement:** if there is an increase of more than 4 points in the FACIT\_Fatigue scale score versus the previous evaluation
- **Maintenance:** if the score on the quality of life scale does not vary by more than 4 points versus the previous evaluation
- **Worsening:** if the score obtained on the Facit\_Fatigue scale decreases by more than four points versus the previous evaluation.

Significant associations will be sought between the habits of daytime rest, the practice of physical aerobic exercise, medication taken, dose and treatment schedule changes, dose interruptions and the number of days of treatment

interruption depending on the evolution in the evaluation of the fatigue in the FACIT\_Fatigue over the last six weeks. The Pearson chi-squared test will be used for this purpose (or Fisher's exact test for 2x2 tables or likelihood ratio test for mxn tables, if necessary).

- Treatment: For each one of the treatment cycles received by patients during the 9-month follow-up, the following will be studied:
  - **Dose change:** the absolute and relative frequency of patients who have changed doses since the last cycle will be provided. In the sub-population of patients with dose changes in the last cycle, their frequency distribution will be presented according to:

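### Each exposure is tested against fatigue or hand-foot syndrome separately at every visit, and no analysis combining visits is specified, so rare exposures are judged on small tables whose scattered results cannot be interpreted

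*SAP*

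**What the plan says.** For FACIT-Fatigue, SAP 8.2.3 classes each patient as improved, maintained or worsened against the previous evaluation, "For each one of the evolution visits (week 6, week 12, week 18, week 24, week 30 and week 36"). It then looks for associations between that class and daytime rest, exercise, medication intake, dose and schedule changes, and interruptions over the preceding six weeks, using chi-square, Fisher or likelihood ratio tests. CTCAE fatigue is handled the same way with a twelve-week look-back. For hand-foot syndrome the associations appear only in the table list, for example "Association between temporary treatment interruptions and evolution of hand-foot syndrome (every three months").

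SAP 9 lists one table per exposure: six for FACIT (3.4.1-3.4.6), six for CTCAE fatigue (3.2.1-3.2.6) and four for hand-foot syndrome (3.1.1-3.1.4). The last FACIT entry is "Association between temporary daytime interruptions and evolution on the Facit_Fatigue (every six weeks"). SAP 4 adds: "The statistical significance value is set to p<0.05". No multiplicity rule is given.

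The only analyses that link visits are the paired tests at the end of SAP 8.2.3 (sign, McNemar, paired t, Wilcoxon), and they contain no exposure. SAP 8.1 and Protocol 7.7 also name independent-sample tests of exposures on fatigue and hand-foot syndrome control, without a time point and without a pooled or repeated-measures method.

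**The concern.** Secondary objective 4 asks what impact breaks, dose reductions and daily habits have on controlling fatigue and hand-foot syndrome. Each patient can supply up to six FACIT intervals, but each planned table uses only one. A break or dose change is uncommon within any single six-week interval, so each table compares a handful of exposed patients, spread over three outcome classes, with everyone else.

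Two things follow. Each table has little power. The reader also receives six unadjusted p-values per exposure with no rule for combining them. If one of six is significant, nothing in the plan says whether that is a finding or chance.

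**Working it through.** **Inputs from the documents.** 100 patients with 5% discontinuation, so 95 (SAP 5.1); six FACIT intervals (SAP 8.2.3); in the sunitinib pivotal trial "38% of patients had to temporarily interrupt treatment, while 50% of patients had to reduce the standard dose", and 30% dose reductions in expanded access (SAP 2); median PFS of 11 months on sunitinib (SAP 2), used as a stand-in for time on treatment.

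**Assumed.** Exposure probability constant over the six intervals; exponential attrition; unexposed patients 20/60/20 improved/maintained/worsened; 40% improved among the exposed; successive changes negatively correlated.

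**Step 1: the plan's own figure.** For a proportion of 10%, n = 1.96² × 0.10 × 0.90 / d². The precision d is not stated. With d = 0.06, n = 3.8416 × 0.09 / 0.0036 = 96.04, rounded up to 97, and 97 / 0.95 = 102.1, rounded up to 103. With d = 0.05 the total is 147 and with d = 0.07 it is 75. So 100 fits about ±6 points on one percentage. It says nothing about the exposure tests.

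**Step 2: exposed patients per six-week table.** Per-interval probability q = 1 − (1 − r)^(1/6). Fraction still on treatment S = 2^(−months/11). Week 6 is 1.38 months (S = 0.917, 87.1 of 95 patients) and week 36 is 8.28 months (S = 0.594, 56.4 patients). The six visits sum to 87.1 + 79.8 + 73.2 + 67.1 + 61.5 + 56.4 = 425.1 patient-intervals.

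| Cumulative rate r | q | Exposed, week 6 | Exposed, week 36 | Total (425.1 × q) |
|---|---|---|---|---|
| 30% (reduction, expanded access) | 0.0577 | 5.0 | 3.3 | 24.5 |
| 38% (interruption) | 0.0766 | 6.7 | 4.3 | 32.6 |
| 50% (reduction, pivotal) | 0.1091 | 9.5 | 6.2 | 46.4 |

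Medians of 8 to 14 months widen the range to 2.8-10.2, hence about 3-10.

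**Step 3: power, by simulation, for 40% against 20% improved.** The comparator is a visit-stratified generalised Cochran-Mantel-Haenszel (CMH) test of the same three classes.

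| Rate | One table | One visit-stratified test |
|---|---|---|
| 30% | from about 12% | about 50% |
| 38% | 13-19% | about 63% |
| 50% | 15-25% | about 76% |

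Other choices for the correlation and for the split of the remaining 60% of exposed patients gave 61-68% and 76-84% for the stratified test in the last two rows. With no effect it rejected in about 5% of studies.

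**Step 4: the six tables as a set.** Six independent tests at 0.05 give 1 − 0.95⁶ = 26.5% with at least one false positive. Sparse tables reject slightly less often, and simulation gives 22-25%. Under the assumed effect, at least one of six is significant in 67-74% of studies at the 38% and 50% rates. Across all outcomes there are 6 × 6 = 36 FACIT tests, 6 × 3 = 18 fatigue tests and 4 × 2 or 4 × 3 = 8-12 hand-foot tests, 62-66 in total.

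**Step 5: a second calculation with a different outcome.** Take worsened yes/no, 30% among the unexposed, 4-9 exposed of 75-90 per table, and a pooled analysis of 478 patient-intervals (24-54 exposed) with design effect 1.5. The single-table ranges span Fisher and chi-square.

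| Worsened, exposed against unexposed | One table | Pooled |
|---|---|---|
| 60% against 30% | 17-47% | 70-94% |
| 50% against 30% | 9-26% | 40-67% |
| 10% against 30% | 0-19% | 36-78% |

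The last row, a protective effect, is the direction that objective 4 asks about.

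**Step 6: scope.** The three-monthly tables hold more exposed patients: from 95 × 0.30 × 3/14 = 6.1 (30% accrued over 14 months) to 95 × 0.50 / 3 = 15.8 (50% over 9 months), so about 6-16. Napping, exercise and intake-time groups need not be small.

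**The case against.** The plan says "This is a descriptive study; therefore, a specific number of patients is not required to calculate the sample size", sets no power target, and only seeks associations. Low power in exploratory tables is then no breach of a promise. This stands as a limit on how serious the point is. It does not remove it, because objective 4 asks about impact and the tables carry p-values against a 0.05 threshold.

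The counts are not the documents' figures. The cited rates are cumulative and come from sunitinib studies, while this study also enrols patients on pazopanib and sorafenib. The SAP counts schedule changes as dose changes and allows repeated interruptions, so real counts could be higher, and early clustering would make some tables fuller and others emptier. This stands, which is why a range is given.

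A reader might infer that a real effect would probably be missed in all six tables and reported as no association. The figures do not support that: at least one table is significant in 67-74% of studies under the assumed effect, and the SAP has no rule that would report such a pattern as no association. The trouble is that 22-25% of studies with no effect also show one. Nor are most real effects missed in general: for 70% against 30% worsened, a single table with 8-9 exposed reaches 56-70% power, and for 50% against 30% pooling also falls short of 80% at design effect 1.5.

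A reader might also infer that the plan rules out any look across visits. The unspecified comparisons in SAP 8.1 and Protocol 7.7 leave that open; the accurate statement is that none is specified.

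Finally, pooling does not cure confounding. SAP 2 describes interruptions and reductions made to control adverse events, so exposure tends to follow worsening. In simulations with no effect, regression to the mean, and breaks two to three times likelier after a worsened interval, the stratified test rejected in about 7-12% of studies. This stands and shapes the fix.

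**Conclusion.** The point holds in this form: exposure tests are specified visit by visit, and no combined exposure analysis appears in either document. For breaks and dose changes in the six-week FACIT tables, power per table is about 12-25%, against about 50-76% for one visit-stratified test, for a rise from 20% to 40% improved. The six unadjusted tables give nearly the sensitivity of one combined test, but at a false-positive rate of 22-25% instead of about 5%, so a scattered result cannot be read either way.

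The size depends on even spread of the cited sunitinib rates, attrition at a median of about 11 months, and the chosen effect. No power claim is made for the habit exposures or the three-monthly tables, although these too lack a combined analysis. The primary description of FACIT-Fatigue is not affected.

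**What to change.** In SAP 8.2.3, make the inferential analysis for each exposure and each outcome (FACIT class, CTCAE fatigue, hand-foot syndrome) one model over all intervals: an ordinal GEE clustered by patient, with a visit term and adjustment for the score or grade at the start of the interval. Report one estimate with a 95% CI per exposure. A visit-stratified CMH test may support it, but its two-degree-of-freedom form gives no estimate with an interval and so cannot stand alone. Keep Tables 3.1.x, 3.2.x and 3.4.x as descriptive counts without significance claims.

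There are two downsides to state. The single estimate averages over visits, so show the visit-specific estimates beside it. It also remains an association: adjusting for the starting score should reduce, but will not remove, the confounding from breaks and reductions made in response to adverse events, and the interpretation should say so.

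The cost is a paragraph of SAP text and one model per exposure and outcome. No new data, visits or patients are needed.

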#### 11 APPENDICES

#### 11.1 ANNEX 1: FATIGUE FACIT QUALITY OF LIFE QUESTIONNAIRE

#### Spanish version of Fatigue FACIT scale (Version 4)

#### Escala FACIT de fatiga (Versión 4)

A continuación encontrará una lista de afirmaciones que otras personas con su misma enfermedad consideran importantes. Marque un solo número por línea para indicar la respuesta que corresponde a los últimos 7 días.

		Nada	Un poco	Algo	Mucho	Muchi- timo
iø.	Me siento agotado(a)	0	1	2	3	4
10 12	Siento debilidad en todo el cuerpo	0	1	2	3	4
Ant	Me siento decaido(a)	0	1	2	3	4
AnZ	Me siento cansado(a)	0	1	2	3	4
Anl	Tengo dificultad para comenzar las cosas porque estoy cansado(a)	0	1	2	3	4
Ant	Tengo dificultad para terminar las cosas porque estoy cansado(a)	0	1	2	3	4
Asi	Tengo energia	0	1	2	3	4
Ast.	Soy capaz de hacer mis actividades habituales (trabajar, ir a la escuela, hacer las compras)	0	1	2	3	4
Ant	Necesito dormir durante el día	0	1	2	3	4
An Li	Estoy demasiado cansado(a) para comer	0	1	2	3	4
An 31	Necesito ayuda para hacer mis actividades habituales	0	1	2	3	4
Aa 25	Estoy frustrado(a) porque estoy demasiado cansado(a) para hacer las cosas que quiero hacer	0	1	2	3	4
4.5	Tengo que limitar mis actividades sociales debido al cansancio	0	1	2	3	4

Spanish (Universal) Copyright1987.1997 17 December 2010 Page 1 of 1

CT24-GSOP-SD-GL04 NI Study SAP Template; Template Version 1.0, Effective 31-Dec-2013 Page 27 of 29

#### Functional Assessment of Chronic Illness Therapy (FAC1T) Fatigue Scale (Version 4)

Below is a list of statements that other people with your illness have said are important. Please circle or mark one number per line to indicate your response as it applies to the past 7 days

		Not at all	A little bit	Somewhat	Quite a bit	Very much
1	I feel fatigued	0	1	2	3	4
2	I feel weak all over	0	1	2	3	4
3	I feel listless ("washed out")	0	1	2	3	4
4	I feel tired	0	1	2	3	4
5	I have trouble starting things because I am tired	0	1	2	3	4
6	I have trouble finishing things because I am tired	0	1	2	3	4
7	I have energy	0	1	2	3	4
8	I am able to do my usual activities	0	1	2	3	4
9	I need to sleep during the day	0	1	2	3	4
10	I am too tired to eat	0	1	2	3	4
11	I need help doing my usual activities	0	1	2	3	4
12	I am frustrated by being too tired to do the things I want to do	0	1	2	3	4
13	I have to limit my social activity because I am tired	0	1	2	3	4

Scoring: Items are scored as follows: 4=Not At all. 3=A Little bit; 2=Somewhat; l=Quite A Bit; 0=Very Much, EXCEPT items #7 and #8 which are reversed scored. Score range 0-52. A score of less than 30 indicates severe fatigue. The higher the score, the better the quality of life.

Item Number	Reverse Item?		Item Response	Item Score
1	4	-		=
2	4	-		=
3	4	-		=
4	4	-		=
5	4	-		=
6	4	-		=
7	0	+		=
8	0	+		=
9	4	-		=
10	4	-		=
11	4	-		=
12	4	-		=
13	4	-		=

Sum individual item scores: \_\_\_\_\_

Multiply by 13:

Divide by number of items answered:

For guidelines on handling missing data and scoring options, please refer to the Administration and Scoring Guidelines on-line at www.facit.org.

Source: Webster, K, Celia, D, & Yost, K. (2003). The functional assessment of chronic illness therapy (FACIT) measurement system: properties, applications and interpretation. *Health and Quality of Life Outcomes*, 1(79), 1-7.

Reprinted with permission from: http://www.facit.org/FACITOrg/Questionnaires

#### 11.2 ANNEX 2. QUALITY OF LIFE - HAND-FOOT SYNDROME

	Skir	n and subcutaneous tis	sue disorders		
		-	Grade	-	-
Adverse Event	1	2	3	4	5
Hypertrichosis	Increase in length, thickness or density of hair that the patient is either able to camouflage by periodic shaving or removal of hairs or is not concerned enough about the overgrowth to use any form of hair removal	usual exposed areas of the body [face (not limited to beard/moustache area)	-	-	-
Definition: A disorder characteri	zed by hair density or length beyor	id the accepted limits of normal in	a particular body region, for a part	cular age or race.	-
Hypohidrosis		Symptomatic; limiting instrumental ADL	Increase in body temperature; limiting self care ADL	Heat stroke	Death
Definition: A disorder characteria	zed by reduced sweating.				
Lipohypertrophy	Asymptomatic and covering <10% BSA	Covering 10 - 30% BSA and associated tendemess; limiting instrumental ADL	Covering >30% BSA and associated tendemess and narcotics or NSAIDs indicated; lipohypertrophy; limiting self care ADL	-	-
Definition: A disorder characteri	zed by hypertrophy of the subcutar	neous adipose tissue at the site of	multiple subcutaneous injections of	of insulin.	
Nail discoloration	Asymptomatic; clinical or diagnostic observations only; intervention not indicated	-	-	-	-
Definition: A disorder characteri	zed by a change in the color of the	nail plate.			-
Nail Ioss	Asymptomatic separation of the nail bed from the nail plate or nail loss	Symptomatic separation of the nail bed from the nail plate or nail loss; limiting instrumental ADL	-	-	-
Definition: A disorder characteri	zed by loss of all or a portion of the	nail.		1	8
Nail ridging	Asymptomatic; dinical or diagnostic observations only; intervention not indicated	-	-	-	-
Definition: A disorder characteri	zed by vertical or horizontal ridges	on the nails.		1	8
Pain of skin	Mild pain	Moderate pain; limiting instrumental ADL	Severe pain; limiting selfcare ADL	-	-
Definition: A disorder characteri	zed by marked discomfort sensatio	n in the skin.			
Palmar-plantar erythrodysesthesia syndrome	Minimal skin changes or dermatitis (e.g., erythema, edema, or hyperkeratosis) without pain	Skin changes (e.g., pæling, blisters, bleeding, edema, or hyperkeratosis) with pain; limiting instrumental ADL	Severe skin changes (e.g., peeling, blisters, bleeding, edema, or hyperkeratosis) with pain; limiting self care ADL	-	-
Definition: A disorder characteri	zed by redness, marked discomfor	t, swelling, and tingling in the palm	ns of the hands or the soles of the f	eet.	
Periorbital oedema	Soft or non-pitting	Indurated or pitting oedema; topical intervention indicated	Oedema associated with visual disturbance; increased intraocular pressure, glaucoma or retinal haemorrhage; optic neuritis; diuretics indicated; operative intervention indicated	-	-
Definition: A disorder characteri	zed by swelling due to an excessiv	e accumulation of fluid around the	orbits of the face.		
Photosensitivity	Painless erythema and erythema covering <10% BSA	Tender erythema covering 10 - 30% BSA	Erythema covering >30% BSA and erythema with blistering; photosensitivity; oral corticosteroid therapy indicated; pain control indicated (e.g., narcotics or NSAIDs)	Life-threatening consequences; urgent intervention indicated	Death
Definition: A disorder characteri	zed by an increase in sensitivity of	the skin tolight.	•	•	•

CT24-GSOP-SD-GL04 NI Study SAP Template; Template Version 1.0, Effective 31-Dec-2013 Page 29 of 29
